5.6 Number of Subjects

[REDACTED] Individual study centers will be allowed to enroll 20% (~60 subjects) of the maximum total trial enrollment without additional approval. Centers may have their maximum enrollment number increased with prior Sponsor [REDACTED]

Clinical Investigation Plan

approval. Enrollment will be limited to a maximum 110 paroxysmal AF cases, 110 early persistent AF (7 days to 3 months duration), and 110 non-early persistent AF (>3 months to 12 months duration) without Sponsor pre-approval.

5.7 Total Expected Duration of the Clinical Investigation

6.0 TREATMENT AND EVALUATION OF ENDPOINTS

The following sections describe the recommended and required procedures for this investigation. Unless otherwise noted, it is recommended that the site follow standard of care for any activities not specifically stated in this CIP.

6.1 Baseline Procedures (within 14 days of index procedure)

The following procedures should be conducted at the baseline visit:

- Document the informed consent process
- Confirm enrollment criteria
- Record height and weight
- Review and record demographics and medical history (including, but not limited to cardiovascular and arrhythmia history)
- Record most recent NYHA assessment
- Record AADs
- Perform transthoracic echocardiogram (TTE)⁴
 - Measure left atrial diameter
 - Measure left atrial volume
 - Measure left ventricular ejection fraction
 - Note any other abnormalities detected
- Complete 12-lead ECG (a previous 12-lead ECG may be used if done within 14 days of index procedure)
- Pregnancy test, if applicable⁵

It is recommended that class I and III AADs be withdrawn 48 hours prior to the ablation procedure to facilitate induction of AF for the mapping protocol (see section 6.2.1).

⁴ If a TTE was performed in the last 6 months and the required data can be collected, this procedure can be skipped at baseline.

⁵ The pregnancy test should follow the site's standard of care prior to the ablation procedure. It does not have to be during the baseline visit. This applies only to subjects who would have a pregnancy test per the sites standard of care (e.g. women of child-bearing potential).

Clinical Investigation Plan

If the subject is identified as pregnant prior to the ablation procedure, they will be identified as a screen failure and the screening log will be updated.

6.2 Index Procedure

The subject should be prepped for an electrophysiology study per the site's standard of care. If there is a thrombus noted the procedure can be delayed up to 90 days post consent until the thrombus has been resolved and the investigator has assessed it to be safe to proceed. In this case, data recorded from the baseline visit will be revisited to note any changes (e.g. updated medical history and medications). If the investigator determines after 90 days the thrombus has not resolved, the subject should be identified as a screen failure and the screening log will be updated.

6.2.1 Mapping Protocol

Prior to any ablation, perform the following steps with the GRID as the only mapping catheter using an HD Wave configuration. HD Wave configuration is defined as any configuration only collecting from electrodes with two orthogonal bi-poles. It is recommended to use the configuration from **Figure 2**. See Appendix VIII for further details.

[figure not shown]

Figure 2 Recommended HD Wave Configuration

Clinical Investigation Plan

- Start recording (F4) an EnSite Segment – label ‘LA geometry’.
- Build LA geometry with GRID.
- End Geometry (F4) collection EnSite recording segment.
- Their first geometry may be a OneMap in sinus rhythm⁶ (SR)
- Then record that segment label “SR OneMap”
- Collect Cardiac Triggered SR Map.
- This is done via Cardiac Triggered AutoMap

- Keep GRID in position for a **recommended 5 cardiac cycles (2 minimum)**

Upon completion, attempt to induce AF⁷, and continue.

- Start a new map in Non- Cardiac Triggered mode (i.e. mapping in AF)
- Set Map Settings of Interior Projection/Exterior Projection to 6/6 mm.**
- Set Map Settings of Interpolation to 6 mm.**

{Consider OneMap to do the geometry collection and mapping}

- Set up Map to collect with GRID.
- Use the CFE Mean map as guidance for map point collection
- CFE Mean: Suggested settings of Sensitivity 0.05 mV (above noise floor). Refractory 80 ms. Width 10 ms.
- Set up CFE Mean map: Suggested CFE Mean Color High of 250 ms and Color Low of 80 ms.
- Set up CFE Mean map with **Segment Length of 8 seconds**.
- Start recording (F4) an EnSite Segment – label ‘LA AF Map’.
- Set Auto Map Criteria as follows. Stable Distance to 5mm. Distance to 3mm.**
- Manually acquire first Auto Map point and then the Auto Map criteria will collect points based on its criteria.

The catheter operator should aim, subject to their own discretion, to color the entire LA geometry using the above Auto Map settings.

⁶ If sinus rhythm cannot be achieved, this map can be captured in another regular rhythm.

⁷ If subject is in AF initially, the AF map can be collected first, then collect the SR map after cardioversion.

Clinical Investigation Plan

- At each anatomical location, catheter operator aims to hold GRID in place for 8 seconds.
- End recording (F4) of Map collection segment.

After the procedure, the complete deidentified EnSite case should be submitted to Abbott per their instructions. This data will be analyzed independently of the investigator for purposes of avoiding bias and ensuring consistent measurements across all sites.

If the procedure is aborted for any reason prior to the collection of at least one voltage map, the subject should be withdrawn from the study. If the operator is not able to achieve pulmonary vein isolation, the subject should be withdrawn from the study once any ongoing serious adverse events have resolved or 30 days, whichever comes first.

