1.0 INTRODUCTION

This document is a clinical investigation plan (CIP) for the WAVE-MAP AF clinical investigation. This clinical investigation is intended to characterize the left atrial substrate using the Advisor™ HD Grid Mapping Catheter, Sensor Enabled™ in an HD Wave configuration and correlate different factors with 12-month success after a single ablation procedure using a pulmonary vein isolation (PVI) approach without further substrate modification. This clinical investigation will be conducted as a post-market study and is intended to support marketing claims for the Advisor™ HD Grid Mapping Catheter, Sensor Enabled™ (GRID).

[REDACTED] This clinical investigation is sponsored by Abbott.

This clinical investigation will be conducted in accordance with this CIP. All investigators involved in the conduct of the clinical investigation will be qualified by education, training, or experience to perform their tasks and this training will be documented appropriately.

1.1 **Background and Rationale**

1.1.1 **Background**

It has been estimated that 20.9 million men and 12.6 million women have Atrial Fibrillation (AF) worldwide.¹² AF has a prevalence of approximately 3% in adults aged 20 years or older.^{3,4} Additionally, one in four middle-aged adults in the US and Europe will develop AF in their lifetime.^{5,6} In Australia, 5% of people aged 55 years or older have AF, and this number is projected to rise to 6% by 2034⁷. These estimates suggest that AF is a condition that impacts a significant number of people with implications for their healthcare systems.

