2.0 CLINICAL INVESTIGATION OVERVIEW

2.1 Clinical Investigation Objectives

The primary objective of this study is to characterize low-voltage substrate, as identified via HD Wave mapping in sinus rhythm, and identify associations with 12-month recurrence rates after a single pulmonary vein isolation (PVI) with a contact force RF ablation catheter.

Other objectives of this study include:

- Analyze additional maps and data collected with GRID and associations with 12-month recurrence rates, such as:

Clinical Investigation Plan

- Voltage maps using different configurations recreated post procedure¹
- Voltage maps using different thresholds for low-voltage
- Fractionation maps

● [REDACTED]

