5.5 Subject Withdrawal

Each enrolled subject shall remain in the clinical investigation until completion of the required follow-up period; however, a subject's participation in any clinical investigation is voluntary and the subject has the right to withdraw at any time without penalty or loss of benefit. Conceivable reasons for discontinuation may include, but not be limited to, the following:

- Subject death
- Subject voluntary withdrawal
- Subject lost-to follow-up as described below
- Subject has a thrombus **and** is withdrawn per Section 6.2
- Index ablation procedure is aborted prior to collection of at least one of the required maps.
- Operator is not able to achieve pulmonary vein isolation.
- Subject becomes a screen failure after consent

Clinical Investigation Plan

The Sponsor must be notified of the reason(s) for subject discontinuation. The site will provide this information to the Sponsor. Investigators must also report this to their respective EC as defined by their institution's procedure(s).

No additional follow-up will be required or data recorded from subjects once withdrawn from the clinical investigation.

However, if a subject withdraws from the investigation due to problems related to the safety or performance of the device under investigation, the investigator shall ask for the subject's permission to follow his/her status/condition outside of the clinical investigation.

In case of subject withdrawal of consent, the site should make attempts to schedule the subject for a final clinical investigation visit. At this final follow-up visit, the subject will undergo the assessments required at the 12-month follow up visit.

If subjects are enrolled into the clinical investigation and are later found to have met exclusion criteria or not all inclusion criteria after the ablation procedure, these subjects will continue follow-up in the clinical investigation and may be included in the analysis population. A protocol deviation must be completed on the applicable CRF. Such subjects identified prior to the index procedure should be identified as screen failures and a protocol deviation is not necessary.

Lost-to-Follow-up

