6.2.2 Treatment Strategy for Ablation

Selected sites use a PVI-only strategy as standard of care for all de novo ablation of AF. After completing the mapping protocol, ablate the pulmonary vein antrum to isolate the veins using a wide area circumferential ablation (WACA) technique⁸ with the TactiCath™ Contact Force Ablation Catheter, Sensor Enabled™ (TactiCath SE). If isthmus dependent flutter is identified and confirmed by electrophysiological testing (e.g. entrainment maneuvers), ablation of the cavo tricuspid isthmus is recommended in the right atrium. No deviations from standard of care⁹ should be performed unless medically necessary. The AutoMark™ feature should be turned on for automated lesion-level data capture based on user-defined settings. Event Markers should be used to note physician comments about changes in rhythm¹⁰.

PVI should be confirmed bidirectionally using the GRID and confirmed after a recommended 20-minute wait time to ensure isolation is achieved. In addition, use of isoproterenol or adenosine are allowed per the investigator's discretion to confirm block.

If arrhythmias remain after pulmonary vein isolation, it is recommended to treat with cardioversion and/or medication unless there is a medical necessity to perform additional ablation.

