### 2.2 Clinical Investigation Objectives

The primary objective of this study is to characterize low-voltage substrate, as identified via HD Wave mapping in sinus rhythm, and identify association with 12-month recurrence rates after a single pulmonary vein isolation (PVI) with a contact force ablation catheter. Other objectives of this study include:

- Analyze additional maps and data collected with GRID and associations with 12-month recurrence rates, such as
  - Voltage maps using different configurations recreated post procedure
  - Voltage maps using different thresholds for low-voltage Fractionation maps

i [REDACTED]

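### Does the SR OneMap label, on a map that may be taken in another regular rhythm, undermine the primary low-voltage measurement?

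*Protocol*

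**What the plan says.** The primary objective in Protocol 2.1 is to "characterize low-voltage substrate, as identified via HD Wave mapping in sinus rhythm" and relate it to recurrence. SAP 2.2 says the same: "characterize low-voltage substrate, as identified via HD Wave mapping in sinus rhythm, and identify association with 12-month recurrence rates".

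Protocol 6.2.1 says the first geometry may be a OneMap in sinus rhythm, with footnote 6 attached, and continues: "Then record that segment label “SR OneMap". Footnote 6 reads: "If sinus rhythm cannot be achieved, this map can be captured in another regular rhythm". The following step collects a cardiac triggered map, also called an SR map, with no segment label of its own. The AF map has its own label, LA AF Map. Footnote 7 deals with subjects who arrive in AF: the AF map may come first, and the SR map follows cardioversion.

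The nearest request for a rhythm note is in Protocol 6.2.2, on ablation: "Event Markers should be used to note physician comments about changes in rhythm". The withdrawal rules name no rhythm. Protocol 5.5 lists "Index ablation procedure is aborted prior to collection of at least one of the required maps" as a reason for discontinuation, and 6.2.1 says of a procedure aborted "prior to the collection of at least one voltage map, the subject should be withdrawn from the study".

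**The concern.** The exposure in the primary analysis is defined by rhythm, yet the protocol allows an exception to that rhythm without asking for the exception to be marked. Read literally, a map in an unnamed regular rhythm carries the same SR name as a true sinus rhythm map. The withdrawal rules do not remove the subject, because any one map is enough to stay in.

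Rhythm can matter for voltage. One study summarised in Protocol Appendix IV reports mean left atrial voltage in paroxysmal patients of 2.24 mV in sinus rhythm and 0.81 mV in AF. Subjects in whom sinus rhythm cannot be reached may also differ in their risk of recurrence, although the documents give no figure for this. Protocol 1.0 says the study is "intended to support marketing claims for the Advisor™ HD Grid Mapping Catheter". If an analyst relied on the label, a result described as low voltage in sinus rhythm would include an unstated number of maps in another rhythm.

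**Working it through.** The plan states no figure to reproduce, and no sample size or power calculation bears on the point. The check is a comparison of texts.

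1. **What the label covers.** Section 6.2.1 names three segments: LA geometry, SR OneMap and LA AF Map. None is for a regular rhythm other than sinus, so the literal claim holds. However, the OneMap step is optional, and the cardiac triggered map that follows has no segment label instruction. Sinus, another regular rhythm and AF share two map labels only where a OneMap is made. The map name SR Map has the same looseness, but it is a name in an instruction.

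2. **Whether the label drives an analysis.** No readable passage says so. Protocol 3.2 has all mapping data analysed centrally by an independent reviewer, and those who take measurements from the maps have no access to the subject's outcome. Section 6.2.1 has the complete deidentified case sent to the sponsor, so the reviewer has the recording as well as its name.

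3. **Whether rhythm is otherwise tracked.** Protocol 4.2 and SAP 2.4.2 list map data in both sinus rhythm and AF, and the lists are open. Rhythm is therefore already a dimension of the map data. Cardioversions and presence of a pacemaker are also collected; they do not record map rhythm but help to interpret it. The case report forms are held separately (Protocol Appendix VII), so a rhythm field can be neither confirmed nor excluded.

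4. **Whether an analysis rule is missing.** The places where it would stand are redacted: Protocol 8.1 and the list for the PTE (per-treatment evaluable) population in 8.2, and SAP 3.1.4, 3.2.1.2 and the matching list in 3.2.4. Absence cannot be inferred.

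5. **Size.** Protocol 5.6 equates 20% of maximum enrolment with about 60 subjects, so the maximum is about 60 / 0.20 = 300. The documents do not give the share of maps taken under footnote 6. The shares below are assumptions, shown only for scale. The intervals use the exact Clopper-Pearson method of SAP 3.1.2, and the last column is 1/√(1 − share) − 1.

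| Assumed share | Maps of 300 | Exact 95% CI | Rise in standard error from the smaller number alone if these maps are left out |
|---|---|---|---|
| 3% | 9 | 1.4% to 5.6% | 1.5% |
| 5% | 15 | 2.8% to 8.1% | 2.6% |
| 10% | 30 | 6.8% to 14.0% | 5.4% |

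The last column ignores any difference in recurrence or voltage between the groups, so the true cost of leaving these maps out could be larger. The bias from keeping them in cannot be calculated. The documents give no voltage for any regular non-sinus rhythm, and the Appendix IV comparison is with AF, which is not a regular rhythm and has its own map and label.

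**The case for a change.** The strongest case for a change is that the gap touches the primary exposure and would cost little to close: name the segment by the rhythm actually mapped, record that rhythm at central review, and report the association with and without the exceptions. No new procedure or data collection would be needed. Footnote 7 does not help, since it changes only the order of the maps, and the Event Marker request sits in the ablation section. With a marketing claim in view, a reader should be able to tell how many sinus rhythm maps really were in sinus rhythm.

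Part of this stands. The name is loose, and a count of maps not in sinus rhythm would be useful in the report. But low cost alone does not justify a change to the plan. The harm depends on someone treating a recording name as evidence of rhythm, and no document says anyone will. A new label would write down what the recording should already show. The suggested SAP text may duplicate what is redacted. SAP 3.3.3 states that no hypothesis testing will be performed, so no formal decision depends on whether a few such maps are kept or left out.

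**Conclusion.** No change to the plan is needed. Protocol 6.2.1 does let a map in another regular rhythm fall under an SR name, and its readable text gives no alternative. That is a detail of naming in an optional step. No pooling, bias or analysis error is shown.

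The conclusion rests on two things the documents state, submission of complete cases and central measurement without access to outcomes, and on one reasonable expectation, that a reviewer with the full case identifies the rhythm of a map before calling it a sinus rhythm map. It would weaken if rhythm could not be recovered from the submitted recordings, or if the redacted analysis rules selected maps by segment name alone; nothing readable suggests either. The number of maps affected is unknown. Footnote 7, which expects an SR map after cardioversion, suggests that footnote 6 is a fallback. The assumed 9 to 30 maps of about 300 illustrate scale and are not an estimate.

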7.3 Adverse Event

7.3.1 Adverse Event Reporting

Safety surveillance and reporting starts as soon as the patient is enrolled in the clinical investigation. Safety surveillance and reporting will continue until the last follow-up visit has been performed, the subject is deceased, the subject concludes participation in the clinical investigation or the subject withdraws from the clinical investigation. Adverse event data, including deaths, will be collected

Clinical Investigation Plan

throughout the time period defined above and will be reported to the Sponsor on a CRF. Additional information with regard to an adverse event should be updated within the appropriate CRF.

Unchanged, chronic, non-worsening, or pre-existing conditions are not AEs and should not be reported.

An offline form will be made available to allow the investigator to report SAEs in the event the entry cannot be made in the EDC. This does not replace the EDC reporting system. All information must still be entered in the EDC system as soon as feasible.

Non-cardiac related abnormal laboratory values will not be considered AEs unless:

1. the investigator determined that the value is clinically significant,
2. the abnormal lab value required intervention, or
3. the abnormal lab value required subject withdrawal from the clinical investigation.

For the purposes of this clinical investigation, the following events will be reported:

- Adverse events that are considered to be related to any of the study devices or the mapping/ablation procedure by the investigator
- Serious adverse events resulting in death

Recurrence of AF, AFL, or AT are not considered reportable adverse events unless they occur in a severity, frequency, or other manner that is significantly worse than the subject's baseline condition. These are considered lack of effectiveness and will be reported as a recurrence on the appropriate case report form.

The investigator should report all SAEs to the Sponsor as soon as possible but no later than outlined below.

SAE Reporting

The investigator should report applicable SAEs to the Sponsor as soon as possible but no later than outlined below.

Clinical Site	Reporting timelines
All Sites	SAEs must be reported to the Sponsor no later than 3 calendar days from the day the site personnel became aware of the event or as per the investigative site's local requirements, if the requirement is more stringent than those outlined above.

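### Subjects aborted before a voltage map are withdrawn with no minimum safety observation, so the course and late consequences of their events may not reach the CRF

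*Protocol*

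**What the plan says.** Protocol section 5.4 counts a subject as enrolled once consent and eligibility are in place and the mapping catheter has entered the vasculature. Section 7.3.1 starts safety surveillance at enrolment. Anything that goes wrong during mapping therefore happens to an enrolled subject under surveillance.

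The last paragraph of section 6.2.1 has two withdrawal rules, one after the other:
- When a case is "aborted for any reason prior to the collection of at least one voltage map, the subject should be withdrawn from the study". No condition or waiting time is attached.
- If isolation cannot be achieved, the subject is "withdrawn from the study once any ongoing serious adverse events have resolved or 30 days, whichever comes first".

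Section 5.5 also lists the aborted procedure as a reason for discontinuation, with a different trigger: "Index ablation procedure is aborted prior to collection of at least one of the required maps". It then states: "No additional follow-up will be required or data recorded from subjects once withdrawn from the clinical investigation". Section 7.3.1 ends safety surveillance when, among other things, "the subject concludes participation in the clinical investigation or the subject withdraws from the clinical investigation". The same section names what is reportable: events related to a study device or to the mapping or ablation procedure, and serious events ending in death.

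Protocol section 8.2 and SAP section 3.2.4 list adverse events for a categorical summary in the Enrolled population. SAP section 3.3.1 rules out imputation.

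**The concern.** The sponsor saw a need to keep one group of early-withdrawn subjects under observation while serious events are ongoing, and wrote that in. The sentence before it covers subjects whose procedure stopped even earlier and contains no such provision. Those stops can be for any reason, and an acute complication is one possible reason. Section 6.2.1 places mapping before any ablation, so by then the subject has been exposed to vascular access and the mapping catheter but not to ablation. The mapping catheter is the device under study, and section 1.0 says the study is meant to support marketing claims for it.

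If the rule is followed as written, the safety record for these subjects can close while an event is still evolving. A later worsening, a delayed related complication or a death would be of the kinds that section 7.3.1 says will be reported, yet nothing requires them to be captured.

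**Working it through.** There is no figure in the plan to reproduce, and the sample-size sections are blacked out. The check sets the provisions side by side and then gives a rough scale.

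**Step 1: observation that each rule guarantees**

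| Group | Source | Observation before exit |
|---|---|---|
| Aborted before a voltage map | 6.2.1, 5.5 | none specified |
| Isolation not achieved | 6.2.1 | until serious events settle, at most 30 days |
| All others | 3.1, 6.4.3 | to the 12-month visit, day 335 to 395 |

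**Step 2: do the first two groups overlap?** Mapping comes before ablation (6.2.1, 6.2.2). A subject aborted before the first map has therefore not had the veins isolated. The second sentence can be read to include that subject, but the first is more specific and has no hold. The text does not say which prevails.

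**Step 3: what is kept and what may be lost.** The event that stops the procedure falls after enrolment and before withdrawal. It is inside the surveillance window, reportable if related, and counted. Only what comes after withdrawal is at risk: resolution, worsening, sequelae, delayed related events and death. The adverse-event summary is a count and percentage, not a censored time-to-event analysis, so an unobserved later event looks the same as no event.

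**Step 4: does another provision restore the data?**
- Section 5.5, withdrawal for device safety or performance problems: "the investigator shall ask for the subject's permission to follow his/her status/condition outside of the clinical investigation". This needs permission, covers one class of reasons, and has no stated route back to the CRF.
- Section 5.5, final visit: applies to withdrawal of consent only.
- Section 6.4.3, status of ongoing events at exit: tied to the 12-month visit, which these subjects do not reach.
- Section 7.3.1, updating event information on the CRF: no period is set, and the same section ends surveillance at withdrawal.
- Section 7.3.2, device complaints: go to the manufacturer and are stated not to be collected on a study CRF.
- Section 11.3, source records: cover event resolution and condition at withdrawal, but set no observation time.

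None of these requires CRF data after withdrawal.

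**Step 5: scale, for illustration only.** Section 5.6 equates 20% of maximum enrolment with about 60 subjects, so N is about 60/0.20 = 300. The documents give no abort-before-map rate, so the rates a below are assumptions. Expected number = 300 × a; chance of at least one = 1 − (1 − a)^300.

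| Assumed a | Expected subjects | Chance of at least one |
|---|---|---|
| 0.25% | 0.75 | 53% |
| 0.5% | 1.5 | 78% |
| 1% | 3 | 95% |
| 2% | 6 | 99.8% |

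These are counts of aborted subjects, not of lost events. The documents give no basis for the share who would have an event after withdrawal.

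**The case against.** The strongest reply is that the second sentence of 6.2.1 already covers aborted subjects, since they too lack isolation, and that the first sentence sets no date for withdrawal, so a site could wait. Both points are fair. They make this an ambiguity between two rules rather than a clear prohibition on follow-up. They do not remove it, because nothing requires a site to take the longer reading.

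A second reply is that the sponsor hears of problems by other routes: complaint reporting, source records and CRF updates. These narrow the gap but, as shown above, do not guarantee study data after withdrawal.

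Third, this is a post-market study of marketed devices used within labelling. Adverse events are listed as additional data, there is no safety endpoint, and SAP section 3.3.3 plans no hypothesis testing. That stands, and it limits the weight of the point.

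A reader might infer that complications which stop a mapping procedure vanish from the safety table, or that the reported event rate is materially too low. The documents do not support either. The stopping event is counted if related. A material shortfall would need many aborted subjects to have a first reportable event only after withdrawal, and the documents give no abort rate, no causes of abort and no rate of delayed events. The view that most such stops are caused by complications, or by the catheter, has no basis in the text either.

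**Conclusion.** The point holds as a conflict between adjacent rules with a limited cost to the safety data. Subjects aborted before a voltage map have no guaranteed safety observation, and data recording ends at withdrawal. Resolution or worsening of the stopping event, a delayed related event or a later death may therefore be missing from the CRF and the adverse-event summary. The number affected is unknown and probably small. The primary endpoint, which is rhythm outcome after a single ablation, is unaffected. This is an inexpensive improvement, not a flaw in the main analysis.

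The verdict rests on two assumptions. Because the population definitions are blacked out, membership of aborted subjects in the Enrolled population is inferred from protocol sections 5.4 and 8.2 and SAP section 3.2.4. The total of about 300 comes from the site cap and is used only for scale.

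The two map triggers, a voltage map in 6.2.1 and a required map in 5.5, are a lesser editorial matter. No subject is shown to be classified differently by them.

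**What to change.** Reconcile protocol sections 6.2.1, 5.5 and 7.3.1 so that, for subjects aborted before a voltage map, adverse events and deaths are collected on the study CRF for at least the period the plan already gives to non-isolated subjects. State which of the two sentences in 6.2.1 governs when both apply, and keep these subjects in the Enrolled adverse-event summary. Use one wording for the map trigger in 5.5 and 6.2.1.

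One detail needs settling in the redraft. The existing hold is tied to an ongoing serious event, so read literally it may give no observation to a subject who has none at the time of the abort. The text should say whether the 30 days applies there too; otherwise delayed events would still be missed.

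This concerns data collection only. It asks for no rhythm follow-up and no change in how subjects are managed. It needs a few sentences in the protocol and a safety contact for a handful of subjects, with no change to the analysis methods.
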